**Table 1. Study Milestones**

Milestone	Planned date
Start of data collection	January 2021
End of data collection	November 2027
Study progress reports	Annually a
Interim analysis b	November 2024
Registration in the EU PAS register	October 2020
Final report of study results	November 2028

EU = European Union; PAS = post-authorization study

a Annual study progress reports to align with scheduled safety reporting requirements, 2021 - 2027.

b An interim analysis will be conducted at year 3 of the study to evaluate patient enrollment and estimate sample size for the study.

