#### **9.5 Study Size**

The sample size was estimated to assess the prevalence of major congenital malformations in infants of women with migraine exposed to erenumab-aooe during pregnancy and associated risk ratio with the internal comparator. Estimated sample size results ranged from 465 to 4,776 in each treatment group (1:1 exposed vs. unexposed internal comparator) to detect risk ratios ranging from 3 to 1.5, respectively ([Table 4](#)). To adequately power an internal comparison of the proportion of major congenital malformation events in the erenumab-aooe exposed, and assuming a 15% drop-out rate and a live birth rate of 62% ([FDA, 2002](#)), 1421 erenumab-aooe exposed pregnant women with migraine would need to be enrolled to observe 749 live births. This sample size would provide 80% power to detect a risk ratio of 2.0 or greater in major congenital malformations relative to an assumed prevalence of 3% in the internal comparator cohort ([CDC, 2008](#)) at a significance level of  $\alpha=0.05$ . Calculations were performed using PASS software version 14.

Given that these numbers assume the prevalence of exposure is sufficient to support recruitment of these numbers, the feasibility of achievement will be re-evaluated at each interim review of the data. The interim analysis planned at year 3 after first patient enrolled and annually thereafter ([Section 9.7.1.1](#)), will include sample size re-estimation, examining the observed prevalence and the risk ratio of major congenital malformations

in the erenumab-aooe exposed compared with the internal comparator, accounting for patient recruitment rates and enrollment projections.

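### Section 9.5 makes the observed malformation risk ratio an input to yearly sample size re-estimation, which can inflate the 5% error rate and gives an unstable target

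*Protocol*

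**What the plan says.** Protocol section 9.5 fixes the design effect in advance. On the target of 749 live births per group it says "This sample size would provide 80% power to detect a risk ratio of 2.0 or greater in major congenital malformations". The reference risk is 3% among unexposed women, and alpha is 0.05. The next paragraph of the same section places interim analyses at year 3 and annually thereafter, and says that these "will include sample size re-estimation, examining the observed prevalence and the risk ratio of major congenital malformations" in the exposed cohort against the internal comparator, taking account of recruitment rates and projections.

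Section 9.1 promises adequate power for a clinically meaningful difference set a priori. Section 7.3 states the primary inference as a risk ratio with a 95% confidence interval and mentions no adjustment for interim use of the data.

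The other descriptions of the interim analysis differ:

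- Table 1, footnote b: "An interim analysis will be conducted at year 3 of the study to evaluate patient enrollment and estimate sample size for the study".
- Sections 9.1 and 9.7.1.2 also mention only the 3-year point.
- Section 6 has year 3 and every year after, for enrollment and futility.
- Section 9.7.1.1 starts at year 3, covers enrollment and the sample size assumptions, and adds a description of primary and secondary outcome data.

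**The concern.** The observed contrast on the primary outcome is named as something that can move the study's size, repeatedly, while the final interval is computed as if the size had been fixed. When the amount of further data depends on the interim effect, a nominal 5% test need not have 5% error, and the matching 95% interval need not have 95% coverage.

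A second problem exists whatever happens to the error rate. At year 3 the ratio would rest on very few malformations, so a target refitted to it would mostly follow chance.

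Third, a size refitted to the observed ratio is no longer a size for the difference that section 9.1 says was chosen in advance. The study answers an FDA requirement, so the coverage of its primary interval and the meaning of its stated power both matter.

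**Working it through.** **1. The plan's own figure.** Inputs from section 9.5: p0 = 0.03, ratio 2.0 so p1 = 0.06, 1:1 groups, 80% power, alpha 0.05, drop-out 15%, live-birth rate 62%. Sidedness is not stated; a two-sided test reproduces the figure.

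n = [z(0.975)·√(2p̄(1−p̄)) + z(0.80)·√(p0(1−p0) + p1(1−p1))]² / (p1 − p0)², with p̄ = 0.045

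= [1.960 × 0.2932 + 0.8416 × 0.2924]² / 0.03² = 0.8207² / 0.0009 = 748.4, so 749 live births per group.

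Enrolled: 749 / (0.85 × 0.62) = 1,421. The formula also reproduces the other rows of Table 4 (2,518 against 2,517 in the first row, the rest exact). A one-sided test would give 590 and a continuity correction 814, so neither was used.

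**2. Information at year 3.** The protocol gives no accrual curve. Assume even accrual over the approximately 7 years: 749 × 3/7 = 321 live births per group, and 321 × 0.03 = 9.6 comparator malformations. At a true ratio of 2.0 (19.3 exposed events) the standard error of the log ratio is √(1/9.63 − 1/321 + 1/19.26 − 1/321) = 0.39. Simulated 5th-95th percentiles of the observed ratio:

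| Live births per group | True ratio 1 | True ratio 2 |
|---|---|---|
| 321 (3/7 of target) | 0.45-2.2 | 1.1-4.2 |
| about 150 (20% of target) | 0.25-4.0 | 0.8-7.0 |

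**3. The refitted target at year 3, true ratio 2.0.** The observed proportions at 321 per group go into the formula of step 1.

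- Both proportions as observed: 10th-90th percentile 272 to 6,725 live births per group.
- Pooled prevalence, ratio held at 2.0: 593 to 994.

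Much of the first range is unattainable. The lower end is below the 321 already observed. At 749/7 = 107 live births per group per year, 6,725 would take about 63 years.

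**4. Error rate at a true ratio of 1.** Simulation assumptions: 3% in both cohorts, pooled z-test at 1.96 at the end, and the target recomputed at each look with the formula of step 1. The rules and caps are assumptions, because the protocol gives none.

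| Assumed use of the interim analysis | Two-sided error |
|---|---|
| Size fixed at 749 | 5.0-5.2% |
| Annual looks, decreases only | 6.0% |
| Annual looks, increases only, cap 1.5 to 4 times 749 | 5.5-7.0% |
| Annual looks, either direction | 6.6-7.9% |
| One look at 3/7, direct refitting | 5.6-7.4% |
| One look, increase only if conditional power is at least 50% | 4.8-5.1% |
| Pooled prevalence, ratio held at 2.0 | 5.0% |

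With looks at 20, 40, 60 and 80% of the target instead, and the size free between 245 and 2,517, the figure is 8.7%. The pooled method keeps about 82% power at a true ratio of 2.0.

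**5. What the pooled method can ask for.** If both cohorts are truly at 3%, a pooled 3% with the ratio held at 2.0 implies 2% against 4%:

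n = [1.960 × 0.2412 + 0.8416 × 0.2408]² / 0.02² = 0.6755² / 0.0004 = 1,141 live births per group, or 1,141 / 0.527 = about 2,165 enrolled.

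**The case against.** A reader might infer that the plan certainly breaks its 5% level. The documents do not support that. Section 9.5 speaks of examining the ratio alongside recruitment; it states no rule, cap or interim test, and no early stop for a positive finding is planned. The error figures belong to assumed rules, and one rule that uses the observed effect holds 5%. The rule and any adjustment may be in the statistical analysis plan, which was not available here, so their absence from the protocol is not itself a fault. This part of the objection stands and limits the claim to a possible inflation.

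Attainability also stands in part. At the assumed accrual, even 1.5 times the target (1,124 per group) would be reached only at 1,124/107 = 10.5 years, and the protocol itself expects low enrollment. Increases of the simulated size are therefore unlikely in a 7-year study. Decreases remain possible, and refitting downward alone gave 6.0%.

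Section 7.3 frames the inference as estimation, and the ENCePP checklist marks the hypothesis item as not applicable. That softens the language of testing but does not remove the issue: the same excess is a loss of coverage in the interval to be reported.

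A reader might also infer that the interim ratio would drive a futility decision. Section 6 ties futility to low participation, and section 9.7.1.1 ties interim actions to recruitment and retention, so that reading is not supported.

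**Conclusion.** The point holds as a poor method that the protocol states, not as a proven failure of error control. Section 9.5 names the observed between-cohort ratio of the primary outcome as an input to yearly re-sizing while keeping an unadjusted 95% interval. Under direct refitting and even accrual, two-sided error can rise from 5% to about 5.5-8%, with coverage falling correspondingly below 95%. The size depends on the assumed rule and cap, and could be nil.

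The instability of the target is the firmer part. It needs only the small event count at year 3, about 10 in the comparator cohort under even accrual and fewer if recruitment lags. Using the observed ratio also displaces the difference that section 9.1 calls a priori.

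The differing descriptions of the interim schedule and purpose are a minor, editorial matter.

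**What to change.** In section 9.5, delete the observed risk ratio as a re-estimation input and hold the target ratio at 2.0. Re-estimate from quantities that do not show the contrast between cohorts: malformation prevalence, live-birth rate and drop-out pooled over both cohorts, the share with first-trimester exposure, and recruitment. Section 9.7.1.1 still has primary outcome data described at the interim, so add there that these data do not set the target.

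If the sponsor wishes to keep the observed ratio, fix in advance the rule, the lower and upper bounds on size, and a final interval that preserves the error rate.

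Reconcile the interim frequency and purpose across section 6, Table 1 footnote b, and sections 9.1, 9.5, 9.7.1.1 and 9.7.1.2.

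The main change is one sentence, with two costs. The target can no longer be tuned to an effect other than 2.0. The pooled method may also call for more than 749 live births per group, about 1,141 if both cohorts are at 3%; if that cannot be recruited, the shortfall can be reported as reduced power.

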**Table 4. Sample Size Calculations**

Risk Ratio	Estimated Sample Size (with 15% Drop-out and 62% Live Birth Rate)	Estimated Live Births (per Group)
1.5	4776	2517
1.75	2326	1226
2.0	1421	749
2.5	731	385
2.75	573	302
3.0	465	245

## **9.6 Data Management**

IQVIA, the CRO, will be responsible for the data management of this study, this includes designing the eCRFs with input and final approval from Amgen, as well as quality checking of the accuracy, completeness and timeliness of data recorded. The CRO will produce a Data Management Quality Plan and a Data Cleaning Plan that describes the quality checking to be performed on the data. Data quality will be enhanced through a series of programmed data quality checks that automatically detect out of range or anomalous data. In the event of discrepant data, the CRO will request data clarification from the CC, which the CC will resolve by providing answers to the data queries electronically in the electronic data capture (EDC) system.

Amgen will perform oversight of the data management of this study, including approval of the CRO data management plans and guidance.

The CC will be responsible for data entry into the EDC system. The CC will receive training and have access to a manual for appropriate eCRF completion. All eCRFs should be completed by designated, trained CC staff. eCRFs will be reviewed and electronically signed and dated by the CC Investigator.

eCRFs and correction documentation will be maintained in the EDC system audit trail. System backups for data stored at the CRO and records retention for the study data will be consistent with the CRO standard procedures. The CRO will comply with Amgen's procedures regarding archiving and record management.

### 9.6.1 Data Quality Assurance

High data quality standards will be maintained, and processes and procedures will be utilized to repeatedly ensure that the data are as clean and accurate as possible when presented for analysis.

Amgen, CRO representative(s), and regulatory authority inspectors are responsible for contacting and visiting the CC for the purpose of inspecting the facilities and, upon request, inspecting the various records of the clinical study (eg, eCRFs and other pertinent data), provided that patient confidentiality is respected. This may also take place remotely by the CRO, as specified in the monitoring plan.

[figure not shown]
The Clinical Monitor or designee is responsible for verifying the eCRFs at regular intervals throughout the study to verify adherence to the protocol, completeness, accuracy, and consistency of the data, as well as adherence to local regulations on the conduct of research. The Clinical Monitor or designee is to have access to patient medical records and other study-related records needed to verify the entries on the eCRFs in accordance with the local laws and regulations.

The Investigator agrees to cooperate with the Clinical Monitor or designee to ensure that any problems detected in the course of these monitoring visits, including delays in completing eCRFs, are resolved.

In accordance with the Sponsor's audit plans, representatives from Amgen's Quality Compliance and Audit function (or designees) may select this study for audit. Review of study-related records will occur to evaluate the study conduct and compliance with the protocol, and applicable regulatory requirements.

See [Figure 1](#) or data flow overview.

Figure 1. Data Flow Overview

CC = coordinating center; CRO = contract research organization; EDC = electronic data capture; HCP = healthcare provider (eg, PCP, neurologist [indication specialist], OB, nurse midwife, pediatrician); OB = obstetrician; PCP = primary care physician

### 9.6.2 Review and Verification of Data Quality

Amgen or designee representatives may conduct remote source data verification (SDV) visits as defined in the Study Monitoring Plan at the study facilities for the purpose of monitoring various aspects of the study. Amgen or designee representatives may confirm that critical protocol data (ie, source data) entered in the eCRF by authorized CC personnel into the EDC are accurate, complete, and verifiable from source documents (eg, questionnaires).

Source documents (paper or electronic) are those in which patient data are recorded and documented for the first time.

Before study initiation, the types of source documents that contain study-relevant information will be clearly defined in the Study Monitoring Plan. The Study Monitoring Plan defines which kind of source data – if available from clinical routine – can be used for documentation into an eCRF.

Source documents that are required to verify the validity and completeness of data entered in the eCRF must not be obliterated or destroyed and must be retained per the policy for retention of records described in [Section 9.8.3](#).

To facilitate SDV, the CC Investigator must provide direct access to applicable source documents and reports for study-related monitoring, Amgen audits, and Institutional Review Board (IRB) review. The participating CC must also allow inspection by applicable health authorities.

## **9.7 Data Analysis**

### **9.7.1 Planned Analyses**

#### **9.7.1.1 Interim Enrollment Assessment**

Regular study updates will be provided in alignment with required safety reporting requirements; anticipated annually. Starting at 3 years following first patient enrolled, an interim analysis will be conducted to assess enrollment and target sample size assumptions, with any needed modifications to patient recruitment and/or retention efforts to be evaluated (see [Section 9.4.4](#)). Included as part of the interim analysis, a report will summarize the number of patients enrolled, erenumab-aooe exposure classification information, and describe primary and secondary outcome data.

#### **9.7.1.2 Primary Analysis**

The final primary analysis will be conducted once all data collection is complete, including up to 21 months of follow-up for enrolled patients. Annual reports for safety reporting requirements will be generated, with an interim analysis at 3 years.

The primary outcome for this study is the comparison between proportions of major congenital malformations in infants of women with migraine exposed to erenumab-aooe during pregnancy with the unexposed internal comparator. All other outcomes will be classified as secondary. Variables identified for the subgroup analysis will be evaluated as potential confounders in the primary comparative analysis of the risk ratio for major congenital malformations in the erenumab-aooe exposed and unexposed internal comparator.

Data analysis for major congenital malformations will be based on the first trimester exposure to erenumab-aooe. Adjudicated major congenital malformations reported up to 1 year of age by the mother or by an HCP will be included in the primary analysis. Women who have received any first trimester prenatal testing after enrollment, with either negative or positive test result will be included in the primary analysis, **except**:

- Women who have received first trimester prenatal screening, in which either aneuploid disorders or genetic disorders that cause major congenital malformations have been detected, because these disorders are unrelated to medication use
- Any prematurity-related disorders and transient conditions
- Women where the outcome is known, prior to enrollment in the registry, either positive or negative, for major congenital malformations that are unrelated to genetic or aneuploid disorders will be analyzed separately as a subgroup analysis.

In addition to the comparison to an unexposed internal comparator cohort, results will be descriptively compared to existing data sources or published reports representing the general population prevalence of birth defects in the general population (see [Section 9.2.1.1.1](#)). Additional external data sources for comparison will be considered as they become available during the study.

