### **9.2.1 Study Population**

Currently pregnant women with clinically confirmed migraine in the U.S. who have been exposed to erenumab-aooe during the 3 months prior to their LMP or at any time during pregnancy will be considered for inclusion in the exposed study cohort. An internal comparator cohort will consist of currently pregnant women with clinically confirmed migraine who have not been exposed to any CGRP mAb, while secondary data sources will be used to compare results to external comparator cohort(s) representing the prevalence of birth defects in the general population (see [Section 9.2.4 Patient Eligibility](#)).

Women will be enrolled prospectively and may be enrolled from the post marketing setting or other clinical or observational studies of erenumab-aooe, unless prohibited by exclusion criteria noted in [Section 9.2.4.2](#). To reduce bias that may occur if outcome information is known prior to enrollment, women should be enrolled in the study as soon

as their pregnancy is known, preferably prior to any informative prenatal testing (where the knowledge of the primary study outcome of the pregnancy would be known – either normal or abnormal), and preferably in the first trimester before 20 weeks gestation. Women who receive any first trimester prenatal screening after enrollment (post-enrollment) will be included in the primary analysis. Decision criteria with regards to prenatal testing before enrollment (pre-enrollment) will be applied to the study population for inclusion into the primary analysis and is outlined in [Section 9.7.1.2](#). [Table 2](#) are the pertinent descriptions.

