**Table 2. Timing and Results of Prenatal Screening Tests: Key Descriptions**

Groups Determined by Test and Result	Inclusion in Analyses
Pre-enrollment prenatal screening: women who have already received prenatal testing where the result is known prior to enrollment	Variable based on subgroup
Subgroup 1: Women who have all normal findings	Included in primary analysis; included in sensitivity analysis of known test result(s) prior to enrollment
Subgroup 2: Women who have pregnancies with aneuploid disorders or genetic disorders that cause major congenital malformations	Excluded from primary and secondary analysis; analyzed as a separate group
Subgroup 3: Women who have pregnancies with results ( normal or abnormal) that are unrelated to aneuploid disorders or genetic disorders that cause major congenital malformations	Included in primary analysis; included in sensitivity analysis of known test result(s) prior to enrollment
Women who had no prenatal screening prior to enrollment in the registry	Included in primary analysis; exclude aneuploid or genetic disorders
Women who had prenatal screening after enrollment in the registry	Included in primary analysis; excluded in primary analysis women who have pregnancies with aneuploid disorders or genetic disorders that cause major congenital malformations

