#### **9.7.2.6 Sensitivity Analysis**

Sensitivity analyses will be performed on both the erenumab-aooe exposed and internal comparator cohorts if sufficient sample size allows, and include but are not limited to the following:

- A sensitivity analysis of major congenital malformations will include women who have received any prenatal screening, regardless of the findings.
- A sensitivity analysis of major congenital malformations will include women where the result is known, regardless of the findings, prior to enrollment in the registry. Subsequently, a sensitivity analysis of major congenital malformations will include women who received any first trimester prenatal screening before enrollment where the result is known to be negative (see [Table 2](#)).
- Sensitivity analyses will also be conducted to study the effects of the timing of erenumab-aooe exposure before and during pregnancy and cumulative exposure periods on each outcome.
- A sensitivity analysis of major and minor congenital malformations will be performed that analyzes different cut points of exposure to erenumab-aooe, accounting for each trimester of exposure. While the primary cut point will be the date of LMP to the end of the first trimester (14 weeks gestation), additional sensitivity cut points will include: 16 weeks prior to LMP through the end of the first trimester, LMP date to the end of pregnancy, 16 weeks prior to LMP to the end of pregnancy, second trimester exposure only, and third trimester exposure only.
- Spontaneous abortions defined as occurring before 22 weeks gestation will also be examined in a sensitivity analysis to account for global variation in the definition for this outcome.
- A sensitivity analysis will be performed to examine the impact of time-varying exposure on primary and secondary outcomes. A time-varying exposure cox regression model will adjust for fixed covariates such as maternal age, presence of comorbidities, previous history of obstetric complications, and gestational age at exposure as time varying covariate. Details will be provided in the SAP.
- For spontaneous abortion, a sensitivity analysis will be performed based on gestational age at enrollment.

Sensitivity analyses may rely on sufficient sample sizes in order to execute. Full details will be described in the SAP.

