#### **9.9.1.2 Information Bias**

Patients who have been informed about a potential adverse pregnancy outcome prior to enrollment in the study may differentially recall their exposures during early pregnancy and may also have changed their exposures after learning of the outcome. This study plans to enroll both women where a fetal diagnosis has been made prior to enrollment in the registry, either positive or negative, for major congenital malformations that are unrelated to genetic or aneuploid disorders), and women with or without prenatal testing prior to enrollment that could determine the status of the fetus) (eg, amniocentesis, genetic testing, nuchal translucency screen, chorionic villus sampling, and late term ultrasound). The differential recall may lead to bias, which will be addressed with the stratification of primary and secondary outcomes by retrospective and prospective status. Additionally, the primary analysis will exclude women who have received first trimester prenatal screening in which either aneuploid disorders or genetic disorders that are known to cause major congenital malformations have been detected.

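### Table 2 and Section 9.7.1.2 define the primary analysis population in conflicting ways for women whose fetal result is known before enrollment

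*Protocol*

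**What the plan says.** Section 9.2.1 states the principle: "Decision criteria with regards to prenatal testing before enrollment (pre-enrollment) will be applied to the study population for inclusion into the primary analysis". It says these criteria are in Section 9.7.1.2 and refers to Table 2 for the descriptions.

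**Table 2** divides women with a known pre-enrollment result into three subgroups. Subgroup 1 has all normal findings. Subgroup 3 has results ("normal or abnormal) that are unrelated to aneuploid disorders or genetic disorders that cause major congenital malformations". For both the entry reads "Included in primary analysis; included in sensitivity analysis of known test result(s) prior to enrollment". Only Subgroup 2, with aneuploid or malformation-causing genetic disorders, is excluded.

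**Section 9.7.1.2** says that women tested in the first trimester after enrollment "with either negative or positive test result will be included in the primary analysis", followed by a list of exceptions. The last of these is "Women where the outcome is known, prior to enrollment in the registry, either positive or negative, for major congenital malformations" unrelated to genetic or aneuploid disorders; they "will be analyzed separately as a subgroup analysis".

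**Section 9.7.2.6** adds: "A sensitivity analysis of major congenital malformations will include women where the result is known, regardless of the findings, prior to enrollment in the registry".

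**Section 9.9.1.2** confirms that the group will exist: "This study plans to enroll both women where a fetal diagnosis has been made prior to enrollment in the registry, either positive or negative". It proposes to handle the resulting recall bias by stratifying outcomes by retrospective and prospective status.

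**The concern.** A woman who enrolls after a scan has shown a non-genetic structural malformation is a primary-outcome case under Table 2 and outside the primary analysis under Section 9.7.1.2. A woman who enrolls after a reassuring malformation scan is likewise in under one rule and out under the other. The primary comparison of major malformations with the internal comparator is the one the study is sized for, so the conflict bears on its main result.

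The group need not be small. Eligibility bars only a known pregnancy loss or live birth, and enrollment before informative testing is a preference (Section 9.2.1). That section also says that outcome information known before enrollment may cause bias.

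The aneuploid/genetic exclusion has a parallel conflict. Sections 9.7.1.2 and 9.7.2.1 tie it to first-trimester screening. Table 2 sets no trimester limit and applies it also to women with no screening before enrollment. Under the rule in Sections 9.7.1.2 and 9.7.2.1, whether a genetic case is removed depends on whether and when the mother was screened.

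**Working it through.** **1. Do other sections settle the population?**

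| Place | What it implies for women with a known, non-genetic pre-enrollment result |
|---|---|
| Table 2, Subgroups 1 and 3 | In the primary analysis |
| 9.7.1.2, exception list | Out; separate subgroup analysis |
| 9.2.1 | Points to both; no precedence |
| 9.7.2.1 | Excludes women only for aneuploid/genetic findings, which fits Table 2 |
| 9.7.2.6 | Fits either: it may add women left out under 9.7.1.2, or be the sensitivity analysis that Table 2 names |
| 9.9.1.2 | A third approach, stratification; the primary exclusion it names is again only aneuploid/genetic |

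They do not.

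**2. The protocol's sample size.** Inputs from Section 9.5: 3% versus 6% (risk ratio 2.0), alpha 0.05 (taken as two-sided), power 80%, 1:1. With mean proportion 0.045:

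n = [1.960·√(2·0.045·0.955) + 0.842·√(0.03·0.97 + 0.06·0.94)]² / 0.03² = 748.4, so 749 live births per group.

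Enrollment = 749 / 0.85 / 0.62 = 1421. Both stated figures reproduce. The only allowances are 15% drop-out and a 62% live birth rate.

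**3. Power if Section 9.7.1.2 governs.** Let f be the share of live births removed in each cohort. The documents do not give f, so it is varied. Power = Φ{[0.03·√n − 1.960·√(2·0.045·0.955)] / √(0.0291 + 0.0564)}, with n = 749(1 − f) rounded down. Enrollment to keep 749 is 749/(1 − f)/0.85/0.62, rounded up.

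| f | n per group | Power | Exposed women to enroll to keep 749 |
|---|---|---|---|
| 0 | 749 | 80.0% | 1421 (as stated) |
| 10% | 674 | 75.8% | 1580 |
| 20% | 599 | 70.7% | 1777 |
| 30% | 524 | 64.9% | 2031 |
| 50% | 374 | 50.8% | 2843 |

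**4. Bias if Table 2 governs.** All inputs here except the 3% risk are assumptions. The true risk ratio is 1.0. A share t of each cohort is tested before enrollment, testing detects a share s of malformations (30% to 50%), and w is the chance that a known-abnormal woman enrolls relative to a known-normal one.

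Risk among tested women: T = 0.03(sw + 1 − s) / [0.03(sw + 1 − s) + 0.97]. Cohort risk: t·T + (1 − t)·0.03.

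Example: t = 50%, s = 50%, w = 2 gives T = 0.045/1.015 = 4.43% and a cohort risk of 3.72%. Against 3% in an untilted comparator, the ratio is 1.24.

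| Scenario (exposed vs comparator) | Null risk ratio, s = 30% to 50% |
|---|---|
| t 50% vs 50%, w 2 vs 1 | 1.14 to 1.24 |
| t 50% vs 50%, w 3 vs 1 | 1.29 to 1.47 |
| t 60% vs 30%, w 0 in both (only known-normal women enroll) | 0.90 to 0.83 |
| t 30% vs 60%, w 0 in both | 1.11 to 1.21 |
| t 60% vs 30%, w 1 in both (no tilt) | 1.00 |
| t 50% vs 50%, w 2 in both | 1.00; prevalence 3.4% to 3.7% in both cohorts |
| t 50% vs 50%, w 0 in both | 1.00; prevalence 2.6% to 2.3% in both cohorts |

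Stacking both imbalances (t 60% vs 30%, w 3 vs 1, s = 50%) gives 1.57.

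**The case against.** Much can be said for the plan.

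- **Recruitment is meant to be comparable.** Section 9.4.4.2 seeks comparators from the same clinical sites, Section 9.9.2 from the same centers where feasible, and Section 9.1 applies the same procedures to both cohorts. A reader might infer from Table 2 that the risk ratio is bound to be biased. The documents do not support that: differential enrollment is plausible but assumed, and with equal testing shares and equal tilt the ratio stays at 1.0.
- **Mitigation is planned.** There are sensitivity analyses, stratification by retrospective and prospective status, and subgroups by testing status and result (Section 9.7.2.1). These would show an effect, but they do not say which analysis is primary.
- **Section 9.2.1 names Section 9.7.1.2 as the home of the criteria.** This leans toward 9.7.1.2, but the same paragraph cites Table 2, whose column assigns women to analyses, and Section 9.7.2.1 agrees with Table 2.
- **The separate subgroup analysis could be additional to inclusion.** Its place in the exception list argues against this. The lead-in does concern testing after enrollment, so the bullet is poorly constructed and needs rewriting in any case.
- **The two groups are not identical.** Table 2 covers any known prenatal result; Section 9.7.1.2 covers knowledge about major malformations. This stands, and it limits the conflict to the overlap, which includes every known non-genetic structural finding.

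**Conclusion.** The concern holds as a contradiction between two definitions, each usable alone. It would be too strong to call the primary population undefined. A statistical analysis plan could choose one rule, but it would then depart from one of the two protocol statements, so the protocol itself needs correcting.

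The contradiction rests on the text alone; its size rests on assumptions. If Table 2 governs, stated power is kept, and a true risk ratio of 1.0 would be estimated at about 0.8 to 1.5 when one imbalance at a time is assumed, and at 1.0 when the cohorts are balanced. With an equal but non-zero tilt, the prevalence and the comparison with the external cohort are still distorted. If Section 9.7.1.2 governs, that source of bias leaves the primary estimate, at a cost in power that depends on the unknown share f.

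**What to change.** Reconcile Table 2 and Sections 9.7.1.2, 9.7.2.1, 9.7.2.6 and 9.9.1.2 to one primary population.

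1. Following Section 9.7.1.2, exclude from the primary analysis only pregnancies with a pre-enrollment result informative for major malformations, normal or abnormal. Put these into the sensitivity analysis.
2. Split Subgroups 1 and 3 of Table 2 on that criterion. Moving them out whole would go too far: Section 9.2.8 and Appendix F count tests such as rubella titer and glucose screening as prenatal testing, and women whose only known results are of that kind should stay in.
3. Define the aneuploid/genetic exclusion by the cause adjudicated by the blinded committee, applied identically in both cohorts whatever test found the disorder and when.
4. State an assumed f and restate power or the enrollment target, because 1421 makes no allowance for this group.

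The first three are wording changes. Appendix F already asks at baseline whether earlier testing gave knowledge of the pregnancy outcome, so much of the needed information is planned for collection. The real cost is a smaller primary set: at f = 30%, either power of 64.9% or about 2031 exposed women instead of 1421, in a registry whose protocol already expects low enrollment.
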